### 5.1.4 Definition of Study Intervention by Study Period

Table [AMAM.5.2](#) provides the study intervention groups to be displayed for each analysis population and analysis period.

[Table AMAM.5.2. Study Intervention Groups](#)

Analysis Population	Analysis Period	Study intervention Groups:
mITT	Study Treatment Period	
 
• 900 miri IV Q4W / 300 miri SC Q4W (adolescent miri)
 

Safety Population	Study Treatment Period	
 
• 900 miri IV Q4W / 300 miri SC Q4W (adolescent miri)
 

Abbreviation: IV = intravenous; miri = mirikizumab; mITT = modified intent-to-treat; SC = subcutaneous.

### 5.1.5 Missing Data Imputation

Intercurrent events (FDA 2017) are events which occur after the study intervention initiation and make it impossible to measure a variable or influence how it should be interpreted. Section [1.1](#) includes intercurrent events for the co-primary endpoints and secondary endpoints which may lead to missing endpoint data based on the estimand of interest:

1. Discontinuation of study intervention prior to time point of interest. Note: participants who take prohibited medications are required to discontinue the study treatment.
2. Specified changes in concomitant CD medications ([Appendix 9](#)) prior to time point of interest.

Participants may also have sporadically missing data due to reasons other than ICEs (e.g., failure to fill out a diary or attend an office visit).

The missing data methods described below will be used to handle missing data.

**Non-Responder Imputation:** As described in Section [1.1](#), the composite strategy will be used to handle binary endpoints; patients who discontinue study treatment or have specified changes in concomitant CD medications are categorized as treatment failures. As such, these patients are not considered missing from the perspective of the estimand of interest. A small number of patients who completed study treatment up to the time point of interest but are sporadically missing the binary endpoint data will still require imputation. These patients will be imputed using nonresponder imputation (NRI).

**Modified Baseline Observation Carried Forward (mBOCF):** As a primary analysis for continuous variables, the analysis of covariance (ANCOVA) with mBOCF approach will be used for handling missing data.

For continuous endpoints, a hybrid estimand strategy is used. For ICEs of study intervention discontinuation and specified changes in the concomitant CD medication, the composite strategy will be used such that measurements after the ICEs will return to baseline. As such, these patients are not considered missing from the perspective of the estimand of interest.

For all participants with sporadically missing observations prior to any ICEs, the last non-missing observation before the sporadically missing data will be carried forward to the corresponding visit.

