#### 9.4.1.2. Estimand

The estimand (ICH 2019) is documented as follows:

The addendum will compare adolescents (15 to <18 years of age) receiving mirikizumab to adults on placebo in individuals with moderately to severely active CD. The specific treatment regimen is explained in Section 6.1. The study population is described in more detail in “Populations for Analysis” (Section 9.3) and the inclusion/exclusion criteria (Sections 5.1 and 5.2).

The primary summary of interest will include descriptive summary of adolescents assigned to the mirikizumab group and adults assigned to the placebo and mirikizumab groups separately for the **CCI** as described in

Section 9.4.1. Additional information concerning the primary and secondary objectives is included in Section 3.

Patients will be considered nonresponders if they discontinue treatment, increase mandatory stable medications, have a disease related surgery, or take prohibited medications prior to the time point of interest (composite approach). The nonresponder imputation (NRI) method will be used as the primary method of accounting for intercurrent events as summarized in “Missing Data Imputation” (Section 9.4.1.3).

Additional details will be provided in the SAP.

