#### **9.4.1.3. Missing Data Imputation**

The missing data methods described will be used to address the intercurrent event strategies proposed for this study. Analysis of categorical efficacy and health outcomes variables will use a NRI method for missing data. A participant will be considered NR for the NRI-based analysis if he or she:

- does not achieve the endpoint(s) being analyzed,
- has missing data at time point of interest that results in non-assessment of an endpoint(s) at the time point of interest,
- discontinues treatment prior to time point of interest,
- specified changes in concomitant CD medications (to be detailed in the SAP).

The NRI method may be used to address missingness when the estimand of interest uses the composite strategy for handling intercurrent events. In this strategy, participants with any of the intercurrent events stated above are defined to have failed study intervention for all subsequent timepoints.

Sensitivity analyses, including additional methods of handling missing data or analyzing the data that may be required to satisfy regulatory needs, will be specified in the SAP.

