9.4.1.3 Missing Data Imputation	
Deleted bullets regarding status of mandatory stable medication use and taking of prohibited medications in defining a participant as a nonresponder.
 
Added text relative to handling of concomitant CD medications and noted specifics will be provided in the SAP.
	
Revision to plan for missing data imputation.
 
Revision to plan for missing data imputation.

9.4.6 Evaluation of Immunogenicity	CCI [REDACTED]	Clarification of sentence to align with analysis approach.
Section 10.2 Appendix 2: Clinical Laboratory Tests	Updated information on exploratory biomarker storage samples.	Separate exploratory biomarkers from nonexploratory biomarkers.
Section 10.6 Appendix 6: Prohibited Medications	
Revised heading for Column 2 of table.
 
CCI [REDACTED]
	
For consistency with adult protocol.
 
For consistency with adult protocol.

	
Added text to include information on IV corticosteroid used for CD that may result in discontinuation.
 
Revised guidance for use of systemic corticosteroids for
	
Allow medical discretion to prevent unnecessary discontinuation.
 
Clarification.

Section # and Name	Description of Change	Brief Rationale
	
non-CD indications.
 
Added information about any nonbiologic investigational therapy.
 
Revised text regarding anti-IL-23p19 antibodies.
 
CCI [REDACTED]
 
Updated abbreviations list.
	
Clarification.
 
For consistency with adult protocol.
 
CCI [REDACTED]
 
To include new additions.

Section 10.7 Appendix 7: Permitted Medications	
Revised table title and revised table column header for Column 2.
 
Revised guidance for use for oral aminosalicylic acids (5-ASAs) and CD-specific antibiotics, oral corticosteroid stabilization, and updated type of permitted vaccines.
	
To align with development program.
 
For consistency with adult protocol.

Section 10.10 Appendix 10 Contraceptive Guidance and Collection of Pregnancy Information	Revised text.	Clarification.
Section 10.11 Appendix 11: Definitions and Selected Abbreviations	Updated the list.	To include new additions.
Section 10.12 Appendix 12: Provisions for Changes in Study Conduct During Exceptional Circumstances	Added appendix.	Provides for temporary changes to procedures intended to be used only during specific time periods as directed by the sponsor in partnership with the investigator.

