## Version history

This Statistical Analysis Plan (SAP) Version 1 for Study I6T-MC-AMAM Adolescent Addendum (AMAM) was based on the protocol dated 08 June 2020 and approved prior to first patient visit.

Version 2 was approved on 02 October 2023, prior to the primary outcome analysis. The following updates were made from Version 1:

1. Updated objectives and endpoints in Section 1.1 to summarize only key efficacy endpoints and removed comparisons to adults, due to the stoppage in enrollments of adolescents. The estimand was updated in accordance with those changes to the objectives and endpoints. Details on the reasoning for the stoppage in enrollment were added as well.
2. Removed references to adult participants in Study AMAM in Section 1.2 as they are no longer relevant because no comparisons are to be performed. Updated diagram of Study Schema to latest version from amendment to the Adolescent Addendum.
3. The statistical hypothesis and multiplicity adjustment subsections in Section 2 were updated to match the updated objectives and endpoints after enrollment was stopped.
4. The sample size determination explanation in Section 3 was updated to reflect the stoppage in enrollment for the adolescents.
5. The ITT population was removed and wording for the Safety population was updated to remove treatment specific language in Section 4.
6. Updated language for analysis methods and baseline definition in Sections 5.1.1. and 5.1.2 to align with changes to SAP from Study AMAM.
7. Removed references to study intervention for adult participants in Section 5.1.4.
8. Updated ICE descriptions, missing data imputation language details for NRI, and added mBOCF method details to Section 5.1.5 to align with changes to SAP from Study AMAM.
9. Updated primary endpoint details in Section 5.3.1
10. Updated analytical approach wording for the primary analysis in Section 5.3.2 and secondary endpoints in Section 5.4.
11. Removed sensitivity analyses in Section 5.3.3
12. Safety analyses for just the induction period were removed in Section 5.6, safety analyses will be provided for the Study Treatment Period only.
13. Summaries of AEs leading to study treatment discontinuation, SAEs, vital signs, hepatic labs, immunogenicity, ISRs, cerebro-cardiovascular events, malignancies and suicidal ideation were updated to be listings in Section 5.6.2, 5.6.4, 5.6.6., 5.6.7.1 , 5.6.7.4, 5.6.7.5, 5.6.7.6, and 5.6.7.7.
14. Box plots removed from laboratory analyses in Section 5.6.3.

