## 1 Introduction

### 1.1 Objectives and Endpoints

The addendum will compare adolescents (15 to <18 years of age) receiving mirikizumab to adults on placebo in individuals with moderately to severely active Crohn's disease (CD).

After enrolling 6 adolescent participants, adolescent enrollment in the Study AMAM addendum was stopped due to slow enrollment and instead enroll pediatric participants in a separate, stand-alone study. Due to the limited number of enrolled participants, there is limited utility in comparisons to adult participants treated with mirikizumab or placebo from Study AMAM. Thus, no comparisons will be performed unless otherwise specified. Instead, descriptive summaries and listings will be provided for specified efficacy endpoints and safety endpoints as described below.

Estimands for the co-primary and secondary endpoints are defined as follows:

- Population: modified intent-to-treat (mITT), defined in Section 4
- Strategies for intercurrent events (ICE) handling are specified below:
  - For binary endpoints, unless otherwise specified, a composite strategy is used where ICEs are included in the endpoint definition. Successful response only if:
    - response criteria from endpoint table met, and
    - no study intervention discontinuation prior to time point of interest, and
    - do not meet any of the specified changes in the concomitant CD medication prior to time point of interest (defined in [Appendix 9](#))
  - For continuous endpoints, a hybrid strategy is used. For ICEs of study intervention discontinuation and specified changes in the concomitant CD medication, the composite strategy will be used such that measurements after the ICEs will return to baseline.

Population-level summary: The proportion of patients achieving the endpoint will be used for binary endpoints and the mean change from baseline will be presented for continuous endpoints.

Objectives	Endpoints
Co-Primary	

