### 5.3.2 Main Analytical Approach

As specified for the primary estimand in Section 1.1, a composite strategy is proposed for other intercurrent events including discontinuing study intervention or having specified changes on concomitant CD medications prior to the time point of interest. The NRI methodology described in Section 5.1.5 will be applied when any of these events occur. This methodology also assumes that missing observations at Week 52 not related to any ICEs will be treated as study intervention failures if the endpoint cannot be evaluated at Week 52.

Primary analyses will consist of descriptive summaries of the efficacy endpoints listed in Section 1.1. Additional details are described in Section 6.2 ([Appendix 2](#)). Note that the details of each analysis will follow the general principles described in Section 5.1.1.

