### 6.3 Appendix 3: Changes to Protocol-Planned Analyses

As compared with the AMAM Adolescent Addendum (15.2), the SAP Version 2 content differs in several respects. The analysis and endpoints describe in the SAP will supersede the language in the protocol.

Due to the early stoppage of enrollment and small number (6) of adolescent participants enrolled, there is limited utility of any comparison to adult participants treated with mirikizumab or placebo from Study AMAM. Thus, no comparisons will be performed. Instead, descriptive summaries will be provided of select key efficacy endpoints. Listings and summaries of safety related endpoints will be provided as well. Details of these listings and summaries are provided in Section 5.

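### Protocol 9.4.1.2 and 9.4.1.3 disagree on whether disease-related surgery and prohibited medication make a patient a nonresponder, and the SAP follows the shorter list

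*SAP*

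**What the plan says.** Protocol 9.4.1.2 (Estimand) sets a composite rule with four triggers: "Patients will be considered nonresponders if they discontinue treatment, increase mandatory stable medications, have a disease related surgery, or take prohibited medications" before the time point of interest. It then points to 9.4.1.3 for the nonresponder imputation that carries the rule out.

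Protocol 9.4.1.3 gives a different list: endpoint not met, missing data, treatment discontinued, and "specified changes in concomitant CD medications (to be detailed in the SAP". Neither surgery nor prohibited medication appears there.

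The SAP has two failure events. SAP 1.1 requires that the patient has not discontinued and that patients "do not meet any of the specified changes in the concomitant CD medication prior to time point of interest". SAP 5.3.2 repeats the pair: "including discontinuing study intervention or having specified changes on concomitant CD medications prior to the time point of interest". SAP 5.1.5 uses the same two and adds, under discontinuation, "Note: participants who take prohibited medications are required to discontinue the study treatment".

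On precedence, SAP Appendix 3 states: "The analysis and endpoints describe in the SAP will supersede the language in the protocol". Item 8 of the SAP version history reads: "Updated ICE descriptions, missing data imputation language details for NRI, and added mBOCF method details to Section 5.1.5 to align with changes to SAP", the SAP meant being that of Study AMAM.

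**The concern.** Two of the four events that the protocol's estimand counts as failure are not failure events in the SAP. Prohibited medication is assumed to be covered because users must stop study drug. Surgery is not mentioned in the composite at all. If a patient can have either event and remain on drug, the two documents classify that patient differently for both co-primary endpoints and for the response and remission secondary endpoints.

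The direction is fixed. Taking events out of a composite can turn a counted failure into an observed result, never the reverse, so these two omissions can only raise a rate or leave it where it is.

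The effect would also be only partly traceable. SAP 5.7 lists CD surgeries by participant, so a reader could find those. No readable SAP section plans a by-participant listing of concomitant medication, and Protocol 9.4.2.3 plans only a summary. SAP 5.3.3 plans no sensitivity analysis.

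**Working it through.** **Step 1: the event lists side by side.**

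| Event | Protocol 9.4.1.2 | Protocol 9.4.1.3 | SAP 1.1, 5.1.5, 5.3.2 |
|---|---|---|---|
| Discontinuation of study drug | yes | yes | yes |
| CD medication changes | yes (increase in mandatory stable medication) | yes (left to the SAP) | yes (SAP Appendix 9) |
| Disease-related surgery | yes | no | no |
| Prohibited medication | yes | no | not a separate event; the remark in 5.1.5 routes it through discontinuation |

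The disagreement therefore starts inside the protocol, and the SAP matches 9.4.1.3. The readable headings of SAP Appendix 9 cover corticosteroids and immunomodulators. Most items under them are redacted, so some prohibited use in those classes may be caught directly.

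**Step 2: does prohibited medication always lead to discontinuation?** The readable protocol text does not say so.
- Protocol 6.5.2 says such patients should be discontinued, and only where the medication is needed to treat CD.
- Protocol 6.5.4 excepts oral 5-ASA compounds and immunomodulators. Immunomodulators have an Appendix 9 heading; 5-ASA has none that can be read.
- Protocol Appendix 12 says that use in exceptional circumstances might not lead to discontinuation. These are temporary provisions.

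**Step 3: can surgery occur without discontinuation?**
- Protocol 7.1.1 lists surgery for active CD as a reason to stop, but introduces the list as possible reasons.
- The same item exempts abscess drainage and seton placement. Whether these are disease-related surgery for the estimand is not settled in any readable text.
- Protocol 7.1.2 allows drug to be withheld and restarted around major surgery, without separating CD surgery from other surgery.

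**Step 4: size.** The plan gives no figure that depends on this rule, so there is none to reproduce. Inputs: 6 enrolled (SAP 3), Wilson 95% intervals (SAP 5.1.1), and the assumption that all 6 were dosed and so are in the mITT population.

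Shift per reclassified patient = 1/n = 1/6 = 16.7 points. If only 5 were dosed, it is 1/5 = 20.0 points.

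Wilson interval: centre = (p + z²/2n)/(1 + z²/n); half-width = z·√[p(1−p)/n + z²/4n²]/(1 + z²/n), with z = 1.96 and z² = 3.841. For n = 6 the divisor is 1 + 3.841/6 = 1.640.
- 3/6: centre (0.500 + 0.320)/1.640 = 0.500; half-width 1.96·√(0.0417 + 0.0267)/1.640 = 0.312; interval 18.8% to 81.2%.
- 2/6: centre (0.333 + 0.320)/1.640 = 0.398; half-width 1.96·√(0.0370 + 0.0267)/1.640 = 0.302; interval 9.7% to 70.0%.

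The effect of one patient who has surgery or prohibited medication, stays on drug and meets the endpoint:

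| Under the SAP | Under Protocol 9.4.1.2 |
|---|---|
| 1/6 = 16.7% (3.0 to 56.4) | 0/6 = 0% (0.0 to 39.0) |
| 3/6 = 50.0% (18.8 to 81.2) | 2/6 = 33.3% (9.7 to 70.0) |
| 6/6 = 100% (61.0 to 100) | 5/6 = 83.3% (43.6 to 97.0) |

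**The case against.** The strongest reply is that the SAP does what the protocol's operational section asks. 9.4.1.2 hands implementation to 9.4.1.3, which names discontinuation and leaves medication changes to the SAP. The history entry for amendment 15.1 shows that the shorter list was deliberate for medication: "Deleted bullets regarding status of mandatory stable medication use and taking of prohibited medications in defining a participant as a nonresponder". The SAP states that it prevails, and its version history discloses that the event descriptions were changed, gives the reason (alignment with the adult AMAM SAP) and dates Version 2 before the primary outcome analysis. A programmer has no doubt about which rule to run.

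Most of that stands. It settles which rule governs, and it rules out reading the shorter list as an unexplained SAP invention or a choice made after results. It does not resolve the conflict. The same amendment history says that the composite approach in 9.4.1.2 was itself updated, so the longer list cannot be dismissed as leftover text. The quoted deletion entry does not mention surgery, and Appendix 3 does not name this departure.

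A second reply is that the gap is hypothetical. Surgery for active CD is a listed reason to stop drug, so such surgery will often already count as failure. Appendix 12 applies only in temporary circumstances, no affected patient is documented, and there are 6 patients with descriptive summaries. That stands too, and it limits the severity.

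A reader might infer that the SAP reaches prohibited medication through discontinuation alone. The documents do not support so strong a reading, because redacted Appendix 9 items may catch some corticosteroid or immunomodulator use.

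**Conclusion.** The point holds as a minor inconsistency with a known direction. Protocol 9.4.1.2 and 9.4.1.3 list different nonresponse events, the SAP implements the shorter list, and the SAP 5.1.5 remark on prohibited medication is firmer than Protocol 6.5.2, 6.5.4 and Appendix 12. A patient with surgery or prohibited medication who stays on drug, and whom Appendix 9 does not catch, would be a nonresponder under 9.4.1.2 yet could be a co-primary responder under the SAP.

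Each such patient who meets the endpoint moves a rate by 16.7 points if all 6 were dosed, or 20.0 points if 5 were. That is simply the weight of one patient, and the number affected may be zero. A reader might infer that the reported rates are inflated, or that CD surgery generally goes uncounted as failure. Neither follows: no such patient is documented, and surgery for active CD is a listed discontinuation reason. The surgical gap is confined to patients who remain on drug, and its extent depends partly on whether abscess drainage and seton placement count.

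**What to change.** In SAP 1.1, 5.1.5 and 5.3.2, add two events to the composite for response and remission endpoints: CD-related surgery, and prohibited medication taken to treat CD, each before the time point of interest and whether or not study drug was stopped. Limiting the second event to CD treatment follows the scope of Protocol 6.5.2 and 7.1.1. It avoids counting every item in Protocol Appendix 6, which includes live vaccines and marijuana. State, for the analysis, whether abscess drainage and seton placement count as surgery.

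Correct the remark in SAP 5.1.5 so that it does not assume discontinuation. Make Protocol 9.4.1.3 match 9.4.1.2, with the scope of prohibited medication worded the same way in both.

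The discontinuation and withholding wording in Protocol 6.5.2, 6.5.4, 7.1.1, 7.1.2 and Appendix 12 must be reconciled with the SAP. No clinical rule is proposed here.

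The cost is a few lines of SAP text and one protocol list. Concomitant medications (Protocol 6.5) and surgeries for CD (Protocol 8.9) are already collected. The downsides are a possibly lower rate and a possible difference from the adult AMAM event list with which SAP Version 2 was aligned. Recording the departure and its reason in SAP Appendix 3 would cost one sentence, but it only documents the difference and would leave the upward direction in place.

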## 5.2 Participant Dispositions

Screen failures and reason for screen failure will be summarized. The number of participants assigned and receiving treatment (that is, participants in the mITT population) will be summarized. Frequency counts and percentages of all participants who are assigned treatment and complete the study intervention, who complete study, who discontinue the study intervention early, and who discontinue the study early will be presented overall. Reasons for early discontinuation of the study intervention and the study will be summarized.

All participants who are assigned treatment (i.e., the mITT population) and discontinued from study intervention or study during any period from the study will be listed, and the timing of discontinuing the study will be reported. If known, a reason for their discontinuation will be provided.

